2.3.2 Secondary Efficacy Endpoints

The secondary efficacy endpoints include the following, in hierarchical order:

- Percent change from Day 1 to Day 84 in non-HDL-C for the obicetrapib 10 mg + ezetimibe 10 mg FDC treatment group compared with the placebo group;
- Percent change from Day 1 to Day 84 in ApoB for the obicetrapib 10 mg + ezetimibe 10 mg FDC treatment group compared with the placebo group;
- Percent change from Day 1 to Day 84 in non-HDL-C for the obicetrapib 10 mg monotherapy treatment group compared with the placebo group;
- Percent change from Day 1 to Day 84 in ApoB for the obicetrapib 10 mg monotherapy treatment group compared with the placebo group;
- Percent change from Day 1 to Day 84 in non-HDL-C for the obicetrapib 10 mg + ezetimibe 10 mg FDC treatment group compared with the ezetimibe 10 mg monotherapy treatment group;
- Percent change from Day 1 to Day 84 in ApoB for the obicetrapib 10 mg + ezetimibe 10 mg FDC treatment group compared with the ezetimibe 10 mg monotherapy treatment group;
- Percent change from Day 1 to Day 84 in non-HDL-C for the obicetrapib 10 mg + ezetimibe 10 mg FDC treatment group compared with the obicetrapib 10 mg monotherapy treatment group; and
- Percent change from Day 1 to Day 84 in ApoB for the obicetrapib 10 mg + ezetimibe 10 mg FDC treatment group compared with the obicetrapib 10 mg monotherapy treatment group.

2.3.3 Exploratory Efficacy Endpoints

The exploratory efficacy endpoints include the following:

- Percent change from Day 1 to Day 84 in VLDL-C, HDL-C, TG, Lp(a), and sdLDL-C for the obicetrapib 10 mg + ezetimibe 10 mg FDC treatment group compared with the placebo group, ezetimibe 10 mg monotherapy treatment group, and obicetrapib 10 mg monotherapy treatment group, and for the obicetarpib 10 mg monotherapy treatment group compared with the placebo group;
- Percent change from Day 1 to Day 84 in particle numbers and size, as measured by NMR analysis, of LDL-C, HDL-C, and VLDL-C for the obicetrapib 10 mg + ezetimibe 10 mg FDC treatment group compared with the placebo group, ezetimibe 10 mg monotherapy treatment group, and obicetrapib 10 mg monotherapy treatment group, and for the obicetarpib 10 mg monotherapy treatment group compared with the placebo group
- Proportion of participants at Day 84 that achieve LDL-C <100 mg/dL (<2.6 mmol/L), LDL-C <70 mg/dL (<1.8 mmol/L), and LDL-C <55 mg/dL (<1.4 mmol/L) for the obicetrapib 10 mg + ezetimibe 10 mg FDC treatment group compared with the placebo group, ezetimibe 10 mg monotherapy treatment group, and obicetrapib 10 mg monotherapy treatment group, and for the obicetarpib 10 mg monotherapy treatment group compared with the placebo group; and
- Percent change from Day 1 to Day 28 in LDL-C for the obicetrapib 10 mg + ezetimibe 10 mg
 FDC treatment group compared with the placebo group, ezetimibe 10 mg monotherapy
 treatment group, and obicetrapib 10 mg monotherapy treatment group, and for obicetrapib 10
 mg monotherapy treatment group compared with the placebo group.

2.3.4 Safety Endpoints

The safety endpoints include the following:

• Safety and tolerability profile of obicetrapib 10 mg + ezetimibe 10 mg FDC therapy, obicetrapib 10 mg as monotherapy, and ezetimibe 10 mg monotherapy assessed clinical laboratory assessments (chemistry, hematology, and coagulation), vital signs, physical examinations, the incidence of AEs and events of special interest.

3 STATISTICAL METHODOLOGY

3.1 General Considerations

3.1.1 Analysis Day

Analysis day will be calculated from the date of first dose of study drug. The day of the first dose of study drug will be Day 1, and the day immediately before Day 1 will be Day -1. There will be no Day 0.

3.1.2 Analysis Visits

Scheduled visits will be assigned to analysis visits as recorded on the CRF.

For each analysis visit, if a scheduled visit occurs within the analysis day window, then the measurement from this scheduled visit will be used. If no scheduled visit occurs or laboratory results of the scheduled visit were unreportable, the unscheduled measurement closest to the target day will be used. If measurements are equidistant to the target day, the later measurement will be used. If laboratory measurements during the scheduled visit were taken while a participant was not in a fasting state and laboratory measurements are available from an unscheduled visit

during which the participant was in a fasting state (and the visit was done within seven days of the scheduled visit), those fasted labs will be utilized in place of the unfasted labs. Otherwise, unscheduled visits will not be re-assigned and will remain labelled as unscheduled.

Early termination (ET) visits will be assigned to analysis visits according to the following visit windows:

Analysis Visit	Target Analysis Day	Low Analysis Day	High Analysis Day
Day 1 (Visit 2)	1	NA	NA
Day 28 (Visit 3)	28	2	56
Day 84 (Visit 4)	84	57	98
Day 112 (Visit 5)	112	99	NA

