5.5.3 Study Drug Administration

Study drugs (2 tablets and 1 capsule) will be administered by the participant orally with water, with or without food, once daily on Day 1 to Day 84 at approximately the same time each morning. On days with visits scheduled, participants should not take the study drugs prior to the visit but should bring the study drugs with them to the site. The study drugs will be administered with water following all fasted blood samples. At Visit 3 (Day 28) and Visit 4 (Day 84), participants will dose from the kit received at the previous visit (Visit 2 [Day 1] and Visit 3 [Day 28], respectively).

If a participant forgets to take the study drugs on a given day, he/she should take the next dose as normal and should not take a double dose to make up for the forgotten dose.

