5.5.4 Treatment Compliance

Compliance with the study drug regimen will be evaluated by counting unused tablets and capsules. Participants will be instructed to bring all unused study drugs to the site at Visit 3 (Day 28) and at Visit 4 (Day 84) (or at an EOT Visit, in cases of early discontinuation of study drug or study). During the Treatment Period, if compliance is not between 80% and 120%, inclusive, the participant will be counselled about the importance of compliance with the regimen.

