3.1.3 Definition of Baseline

Baseline is defined as the last measurement prior to the first dose of study drug, unless otherwise stated.

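### SAP 3.1.2 picks a replacement Day 84 LDL-C sample without reference to the last dose, so an off-drug redraw can become a completer's Day 84 value

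*SAP*

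**What the plan says.** **Substitution rules (SAP 3.1.2).** There are two routes.

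- *Non-fasted scheduled sample.* If a fasted unscheduled sample exists, "those fasted labs will be utilized in place of the unfasted labs", provided "the visit was done within seven days of the scheduled visit".
- *Absent or unreportable scheduled sample.* Here "the unscheduled measurement closest to the target day will be used". On ties: "If measurements are equidistant to the target day, the later measurement will be used".

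The window table that follows (Day 84: Days 57 to 98) is introduced for a different purpose: "Early termination (ET) visits will be assigned to analysis visits according to the following visit windows". Neither route refers to the first or last dose.

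**Dosing around Visit 4.** Protocol 5.5.3 has drug taken "once daily on Day 1 to Day 84 at approximately the same time each morning", and on visit days the dose follows the fasted blood samples. Protocol 5.5.4 has unused drug brought back at Visit 4.

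**Provisions that reduce the problem.** Protocol 7.1.2 asks the site to reschedule a visit when the participant is not fasting. Protocol 5.5.2 supplies 16 spare days of drug in case Visit 4 is postponed.

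**Use in the analysis (SAP 3.4.1).** The primary analysis uses LDL-C by preparative ultracentrifugation (PUC) and treats the value as missing without it. Participants who stayed on treatment and have a Day 84 value form imputation group (1), taken as observed. Those with a missing value, and those who discontinued treatment but have a value, form group (2).

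**Baseline (SAP 3.1.3).** "Baseline is defined as the last measurement prior to the first dose of study drug, unless otherwise stated".

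**The concern.** The primary objective is LDL-C at Day 84 of a 12-week daily regimen. A redraw several days after a completed Visit 4 measures LDL-C after dosing has stopped, yet it carries the Day 84 label.

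Nothing elsewhere in the plan catches this:

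- SAP 3.4.1 lists two intercurrent events, treatment discontinuation and prohibited medication use. A completer has neither, so the treatment policy strategy gives no reason to prefer an off-drug value to an on-drug one.
- The secondary, hypothetical estimand excludes values after study drug discontinuation. A completer's redraw is not flagged as such and stays in.
- The mITT On-Treatment Population is filtered on the obicetrapib concentration at Visit 4. An LDL-C redraw taken afterwards can pass that filter.

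The third sensitivity analysis (last observation carried forward) does restrict itself to on-treatment measurements, so the SAP already uses the concept; 3.1.2 omits it.

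At stake is some dilution of the active-arm effects. All four co-primary comparisons must succeed, and FDC versus obicetrapib has the least room.

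**Working it through.** **1. When is a redraw off drug?** Suppose Visit 4 takes place on Day 84. Blood is drawn, the dose is taken, and unused drug goes back.

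- Redraw on Day 85: about one dosing interval after the last dose, comparable to a normal trough.
- Redraw from Day 86 onward: beyond one dosing interval, so off drug. The non-fasted route allows up to Day 91 (84 + 7).
- Unreportable route: no limit is stated. If the early-termination window were borrowed, it would still allow Day 98, which is 98 − 84 = 14 days after the last dose.
- Tie: if the scheduled result is unreportable and there are unscheduled draws on Days 82 and 86, both are 2 days from target. The rule takes Day 86 (off drug) over Day 82 (on drug).

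**2. The plan's own power figures.** Inputs from SAP 2.2.2: 95 evaluable per arm, SD 25, one-sided 0.025. The standard error of a difference is 25 × √(2/95) ≈ 3.63 points, and power = Φ(δ/3.63 − 1.96).

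| Comparison | δ (points) | Power |
|---|---|---|
| FDC vs placebo | 30 | >99.9% |
| FDC vs ezetimibe | 20 | 99.98% |
| Obicetrapib vs placebo | 15 | 98.5% |
| FDC vs obicetrapib | 12 | 91.1% (noncentral t: 90.8%) |

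Each stated claim of more than 90% reproduces.

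**3. Size of the dilution.** Let f be the share of participants whose Day 84 value is an off-drug redraw and l the share of effect lost by then. The documents give neither. I assume f = 2% to 5% and l = 25% to 50%, the same in every arm.

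- Per swapped FDC participant, on a 30-point effect: 30 × 0.25 = 7.5 to 30 × 0.50 = 15 points.
- FDC-arm mean: 7.5 × 0.02 = 0.15 to 15 × 0.05 = 0.75 points.
- 12-point comparison, δ × (1 − f × l): 12 × (1 − 0.02 × 0.25) = 11.94, power about 90.9%; 12 × (1 − 0.05 × 0.50) = 11.70, power 89.7%.

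**4. Wider range for the 12-point comparison, assuming total loss of effect (l = 100%).**

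| f | Difference (points) | Power |
|---|---|---|
| 2% | 11.76 | 90.0% |
| 5% | 11.40 | 88.2% |
| 10% | 10.80 | 84.6% |

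The other three comparisons stay at 96% or above throughout.

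**The case against.** **The case for leaving the rule alone.**

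- The protocol tells sites to reschedule a non-fasting visit and supplies drug to cover the delay, so few redraws should follow a completed Visit 4. This is fair, but it works only if the problem is noticed before blood is taken. The SAP rule is written for samples already drawn, and an unreportable result is known only afterwards.
- A next-day redraw is still at trough, and the rule also accepts draws before the visit. Both are correct: the concern covers only redraws beyond about a day after the last dose.
- The tie needs two unscheduled draws as well as an absent or unreportable Visit 4. If Visit 4 was not held, spare supply may keep the later draw on drug. So the tie will be rare.
- It is not established that a swap discards a PUC result for another PUC result. PUC is specified for everyone only at Day 1, Day 84 and EOT, and unscheduled procedures depend on the reason for the visit. This is a further gap: if the swap is made and the redraw has no PUC, the primary value becomes missing and a completer moves to group (2).
- Protocol 7.1.2 requires fasting samples, so preferring the fasted redraw is a defensible ordering. This is a real trade-off and the main cost of the fix.
- The effect is small against a standard error of about 3.63 points and, with similar redraw rates across arms, runs toward the null. Both stand and limit the importance of the point.

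**A stronger reading to avoid.** A reader might infer that the same swap lets an on-drug sample from the days after first dose become the primary baseline, since the endpoint is worded from Day 1. The documents do not support this. SAP 3.1.3 and Protocol 9.2 fix baseline as pre-dose, and the estimand calculation, the ANCOVA covariate and the imputation model all use Baseline. What remains is loose wording: the endpoint title, the exception clause in 3.1.3, and mITT membership tied to Day 1 data.

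**Conclusion.** The point holds for Day 84. SAP 3.1.2 allows an off-drug redraw to replace an on-drug non-fasted result within seven days, or to fill in for an unreportable one with no stated day limit. The participant is then analysed as an ordinary observed completer.

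The consequence is a dilution toward the null that is probably small: about 0.15 to 0.75 points on the FDC arm, and up to about 1.4 percentage points of power on the 12-point comparison (91.1 − 89.7). These sizes rest on assumed redraw rates and an assumed loss of effect. The 14-day ezetimibe exclusion before Screening is an eligibility rule; it says nothing about day 7 and nothing about obicetrapib, so it does not supply the missing figure.

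This does not threaten the trial's conclusions. It is worth correcting because the change is specific and inexpensive.

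**What to change.** Amend SAP 3.1.2 before unblinding:

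1. **Reportable but non-fasted Day 84 sample.** Let a fasted redraw replace the scheduled PUC value only if the redraw has a PUC result and was drawn no later than the day after the last dose, or if the participant had already stopped drug early. Otherwise keep the scheduled PUC value and use the fasted redraw in a sensitivity analysis.
2. **Absent or unreportable scheduled result.** State a day limit for the redraw and prefer an on-treatment draw. Do not set an available redraw within that limit to missing. Doing so would put a completer in group (2), where the value is modelled from participants who stopped treatment or, under the fallback, from placebo. That could dilute the effect more than the redraw would.
3. **Ties.** Break them toward the on-treatment, earlier draw.
4. **Baseline.** State that 3.1.2 never overrides the pre-dose baseline in 3.1.3.

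The cost is a few sentences. SAP 3.3.7 already uses the last-dose date for exposure, so the condition can be programmed from existing data. The downside is that a few non-fasted PUC values stay in the main analysis, which the sensitivity analysis in item 1 addresses.

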8.1.4.1 Guidelines for management of elevated liver enzymes

Participants with signs or symptoms consistent with liver injury (eg, nausea, vomiting, anorexia, fatigue, or right upper abdominal pain or discomfort) should undergo immediate testing of ALT, AST, gamma-glutamyl transferase, bilirubin, alkaline phosphatase, prothrombin time, and international normalized ratio.

In the absence of clinical symptoms, participants with ALT or AST $>3 \times ULN$ (if normal at baseline) or >2-fold change (if abnormal at baseline) should be retested within 48 to 72 hours for the usual serum measurements (ALT, AST, alkaline phosphatase, and bilirubin) to confirm the abnormalities and to determine if the associated values are increasing or decreasing. There should also be an inquiry about symptoms at the time of follow-up.

If the above abnormalities are confirmed:

- Repeat liver enzyme and serum bilirubin tests 2 or 3 times weekly. The frequency of retesting can decrease to once a week or less if abnormalities stabilize or the study drug has been discontinued and the participant is asymptomatic;
- Obtain a more detailed history of symptoms and prior or concurrent diseases;
- Obtain a history of concomitant drug use (including nonprescription medications and herbal and dietary supplement preparations), alcohol use, recreational drug use, and special diet;
- Rule out acute viral hepatitis types A, B, C, D, and E; autoimmune or alcoholic hepatitis; nonalcoholic steatohepatitis; hypoxic/ischemic hepatopathy; and biliary tract disease;
- Obtain a history of exposure to environmental chemical agents;
- Obtain additional tests to evaluate liver function, as appropriate (eg, international normalized ratio, direct bilirubin); and
- Consider gastroenterology or hepatology consultations.

Study drug discontinuation should occur if:

- ALT or AST $> 8 \times ULN$;
- ALT or AST >5 × ULN for more than 2 weeks;
- ALT or AST >3 × ULN and total bilirubin >2 × ULN or international normalized ratio >1.5; or
- ALT or AST $>3 \times$ ULN with the appearance of fatigue, nausea, vomiting, right upper quadrant pain or tenderness, fever, rash, and/or eosinophilia (>5%).

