3.5.2 Event of Special Interest

Events of special interest (ESIs) include the following: hepatic abnormalities, muscle-related abnormalities, new-onset diabetes mellitus (NODM) and/or hyperglycemia, renal abnormalities, changes to antihypertensive medication(s) due to changes in blood pressure, and macular degeneration described as follows:

- AST or ALT > 3×ULN;
- Total bilirubin > 2×ULN;
- Creatine kinase (CK) > 5 × ULN;
- NODM or worsening of glycemic control;

Note: NODM is defined by 1 or more of the following criteria, based upon information from AE, medication, and laboratory data:

- AE indicating new type 1 or type 2 diabetes;
- Initiation of anti-diabetes medication with confirmation of the diagnosis of diabetes by blinded external review by experts in diabetology;
- HbA1c ≥6.5% (≥0.065 hemoglobin fraction); and/or
- Two consecutive values of fasting plasma glucose that are ≥126 mg/dL (≥7.0 mmol/L).

Note: Worsening of glycemic control will be defined as HbA1c increase from baseline >0.5% (>0.005 hemoglobin fraction) and/or a new concomitant medication or increase in current antidiabetic therapy in a participant with a baseline HbA1c \ge 6.5% (\ge 0.065 hemoglobin fraction)

- A >25% decrease in eGFR from Baseline or an eGFR<30mL/min/1.73 m², calculated using the Chronic Kidney Disease Epidemiology Collaboration equation, and/or an increase in serum creatinine of ≥0.3 mg/dL (≥26.5 µmol/L) from baseline;
- Changes to antihypertensive medication(s) due to changes in blood pressure in those participants receiving antihypertensive medication(s) treatment at baseline, and new

antihypertensive medication prescriptions for participants not previously treated for hypertension; and

Macular degeneration.

Values and changes from baseline will be summarized for ALT, AST, and total bilirubin by visit and treatment group. The number and percent of participants with abnormal values for ALT, AST, and total bilirubin will be summarized. These summaries of participants with abnormal values will be performed overall; by normal Baseline; and by abnormal Baseline for ALT, AST, and total bilirubin individually.

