3.5.3 Clinical Laboratory Tests

Blood samples for clinical laboratory evaluations (chemistry, hematology, and coagulation) will be collected at visits specified in Table 1. Blood samples for chemistry and hematology must be obtained under fasting conditions (ie, after the participant has fasted for a minimum of 8 hours) and before study drug administration. For the purposes of this study, fasting will be defined as nothing by mouth except water and any essential medications. See Appendix B of the protocol for a complete list of analytes.

Laboratory values will be summarized descriptively, including the change from baseline. In addition, shift tables for select parameters will be presented to describe the change in laboratory parameter values at post-baseline visits using normal range categories (low, normal, and high).

Chemistry and hematology laboratory parameters will be listed.

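### SAP 3.1.2 keeps some exit and symptom-prompted safety results out of the by-visit and general shift tables, and no worst post-baseline summary makes up for it

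*SAP*

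**What the plan says.** SAP 3.1.2 sets three rules that matter here.

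- **Early termination.** "Early termination (ET) visits will be assigned to analysis visits according to the following visit windows". The Day 28 row reads "Day 28 (Visit 3) 28 2 56": target day, lowest day, highest day. Days 57-98 go to Day 84, and Day 99 onward goes to Day 112.
- **Priority.** "For each analysis visit, if a scheduled visit occurs within the analysis day window, then the measurement from this scheduled visit will be used".
- **Unscheduled results.** These are used if no scheduled visit occurred, if the scheduled labs were unreportable, or if fasted unscheduled labs within seven days can replace unfasted scheduled ones. Beyond those three cases, "Otherwise, unscheduled visits will not be re-assigned and will remain labelled as unscheduled".

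The safety tables are then mostly built on analysis visits. In SAP 3.5.2, "Values and changes from baseline will be summarized for ALT, AST, and total bilirubin by visit and treatment group", and CK is handled the same way. In SAP 3.5.3 the general laboratory shift tables are meant "to describe the change in laboratory parameter values at post-baseline visits using normal range categories". SAP 3.5.4 summarizes vital signs at each visit.

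Some outputs in SAP 3.5.2 are not by visit. The eGFR and urine albumin-creatinine shift tables and one CK summary run from baseline to EOT. The counts of participants with abnormal ALT, AST, bilirubin or CK are made overall and by baseline status.

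**The concern.** A participant who attends Visit 3 and withdraws on, say, Day 45 can have two records competing for Day 28. The scheduled one is kept, so the exit chemistry, hematology and vital signs appear in no by-visit row. These are the last safety values of someone who left the study.

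Liver tests prompted by symptoms between visits (Protocol 8.1.4.1) are unscheduled. When the neighbouring scheduled visits are usable, the three exceptions do not apply and the results stay outside the analysis visits. Once a liver abnormality is confirmed, the same section calls for frequent further testing: "Repeat liver enzyme and serum bilirubin tests 2 or 3 times weekly". Those results are unscheduled too.

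At stake is whether the tables that compare arms on laboratory values reflect results taken because something was wrong. Listings keep each value but do not summarize by arm.

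**Working it through.** The plan states no figure on this point, so there is none to reproduce. The check applies the window table and then sizes the group affected.

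**1. The windows are deliberate.** The upper limits are midpoints between target days: (28 + 84)/2 = 56 and (84 + 112)/2 = 98. Every ET day from 29 to 56 falls in the Day 28 window.

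**2. Does Visit 3 displace the ET record?** The SAP gives no explicit ET-versus-scheduled tie-break, so two readings were tried.
- Scheduled first (the plain reading): Visit 3 supplies Day 28 for any ET visit on Days 29-56.
- Closest to target: Visit 3 has a window of ±7 days, so if held in window it is at most 7 days from Day 28. An ET visit on Days 36-56 is 8 to 28 days away and still loses. Only Days 29-35 could come out differently.

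If Visit 3 was missed, the ET record can fill Day 28. ET visits on Days 57-98 go to Day 84 and are kept. Coagulation and HbA1c are not drawn at Visit 3 (Protocol Appendix A), so for them no Visit 3 value competes. Their ET result would sit in a Day 28 row that has no scheduled counterpart.

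**3. Size of the ET part.** Inputs: about 400 participants and about 5% dropout (SAP 2.2.2). Assumption: dropouts are spread evenly over Days 1-84.
- Dropouts: 0.05 × 400 = 20.
- On Days 29-56 (28 days): 20 × 28/84 = 6.7, or 1.7% of 400.
- On Days 36-56 only (21 days): 20 × 21/84 = 5.
- With an assumed 3% dropout: 12 × 28/84 = 4. With 10%: 40 × 28/84 = 13.3.

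These are upper bounds. Each person must withdraw from the study, attend the EOT visit and have a usable Visit 3. Protocol 4.5 only recommends the EOT visit for withdrawals. Appendix A, footnote c, gives no EOT visit to those who stop drug between Visits 3 and 4 but stay in the study.

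**4. Unscheduled results.** The documents give no rate of symptom-driven testing, so this part cannot be sized.

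**5. Which outputs are affected?**
- By-visit laboratory and vital-sign tables: the displaced ET record is absent. The by-visit laboratory tables also omit unscheduled results outside the three exceptions.
- General laboratory shift tables (3.5.3): the same, because they use post-baseline visits.
- Baseline-to-EOT outputs (eGFR, albumin-creatinine ratio, CK): undetermined. EOT is not an analysis visit in 3.1.2, which speaks of ET. SAP 3.5.5 pairs Visit 4 with EOT, but only for physical examinations.
- Abnormal-value counts: undetermined. The eligible records are not stated.
- A worst post-baseline summary: none is planned.

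**The case against.** The strongest reply is that little is hidden. Using one scheduled record per visit is a normal convention for by-visit summaries. All data are listed (SAP section 6). Clinically significant laboratory abnormalities are reportable as adverse events (Protocol 8.1) and so reach the adverse-event tables. The abnormal-value counts are per participant and the special-interest thresholds apply to values; neither is limited to analysis visits. The output is descriptive, and worst-value tables favour finding extremes in participants who are tested more often.

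Much of this stands, and it rules out stronger readings that a reader might infer.

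- **That reported abnormality rates are understated throughout.** Nothing in the SAP excludes unscheduled or ET results from the abnormal-value counts. The SAP is silent on which records are eligible.
- **That confirmatory retests are lost evidence.** A retest after an abnormal scheduled value hides nothing, because the triggering value is already in the tables. Only tests first prompted between visits matter here.
- **That all shift tables are affected.** The eGFR and albumin-creatinine tables run to EOT.
- **That the 56-day gap between Visits 3 and 4 measures the loss.** A 14-day excursion starting at random in that gap misses both draws with probability (56 − 14)/56 = 75%. That describes the visit schedule. Without symptoms such an excursion may prompt no test at all, and a table rule would not recover it.

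The reply does not meet the narrower point. For the by-visit and general shift tables, the written rule sets aside collected values, and no planned summary is stated to bring them back.

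**Conclusion.** The point holds in a limited form. Followed as written, SAP 3.1.2 keeps two kinds of result out of the by-visit safety tables and the general laboratory shift tables: exit results on Days 29-56 when Visit 3 is usable, and laboratory results first prompted by symptoms between visits when no exception applies. Two matters are left open: how EOT is derived for the baseline-to-EOT outputs, and which records feed the abnormal ALT, AST, bilirubin and CK counts.

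The ET part is small: at most about 7 of 400 participants, or 4 to 13 across the assumed 3% to 10% dropout range. That rests on even timing of dropout, attendance at the exit visit and the plain reading of the priority rule. The symptom-driven part has no size that the documents can supply. No efficacy conclusion depends on this. The change is still worth making, because the values are already collected and the safety tables are where arms are compared.

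**What to change.** - **SAP 3.1.2:** keep ET and EOT safety results as a separate EOT safety analysis visit, so that Visit 3 cannot displace them. Use that visit for the baseline-to-EOT tables in 3.5.2.
- **SAP 3.5.2 and 3.5.3:** base the general shift tables and the abnormal ALT, AST, bilirubin and CK counts on the worst post-baseline value across scheduled, unscheduled and ET/EOT records. Present them beside the by-visit summaries.

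The cost is SAP wording and one derived worst-value flag in the laboratory analysis data, with no new data collection. The downside is that participants tested more often have more chances of an extreme value, so the by-visit tables should stay as a companion.
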